8.1.1 Primary Objectives

For pilot testing of the tool in Aim 2, we will collect demographic information and measure decisional conflict, change in decision self-efficacy, change in knowledge about HCV treatment risks and benefits among patients with advanced CKD, DA usability, and the match between patients’ intended choice and their stated preferences.

8.2 Bias

8.2.1 Methods to Minimize Bias

During the pilot phase (Aim 2), there is a chance of social desirability bias occurring. Social desirability bias is a type of response bias where participants give answers that are more favorable to the interviewer. We will reduce this bias by choosing the wording for our questions and materials carefully, using validated measures when available for Aim 2, assuring them there are no right or wrong answers, and reminding them that we are here to learn from them.

Confounding is often mentioned as a “mixing of effects” wherein the effects of the exposure under study on a given outcome are mixed in with the effects of an additional factor (or set of factors) resulting in a misrepresentation of the true relationship [61]. We controlled for confounding during study planning, where we specified our inclusion criteria and will control at the time of analysis by computing a multi-variable regression analysis.

We also selected a repeated measures/within subject design to minimize potential bias of a randomized trial randomizing at the patient level, where clinicians could contaminate the control group if they learned communication techniques after using the DA and applied them to controls as well.

8.2.3 Limitations

- Aim 2 is a single site study with a moderate sample size, so results might not be generalizable. To address this, we plan to include a national sample of clinicians in Aim 3.
- Since there is no use of randomization in Aim 2, results should be interpreted as demonstrating preliminary efficacy of the tool. For example, we will not know if there were learning effects of taking the same measures twice or whether the DA led to changes in pre-post test outcomes. We will compare results to other studies of DAs and will design future larger studies with a control group for comparison.

8.3 Sample Size and Power Calculations

Sample size and power were calculated using Power Analysis and Sample Size Software (PASS 11) [53]. We conducted our sample size calculation based on our expected change in decisional conflict based on past studies using DAs overall [54], and by consulting with the scale's user manual [55]. We expect a 15 point reduction in decisional conflict scores pre- and post- use of the DA and an effect size of 0.35. To examine within group differences in decisional conflict among patients pre- and post-use of the DA, we will conduct a paired-samples t-test. A sample size of 70 patients allows us to achieve a power of 80%, using two-sided t-test with a type I error of 5%.

We will also examine within group differences in our outcomes among patients pre- and post-use of the DA in a multivariable linear regression model controlling for up to 5 independent covariates (e.g. age, health literacy, race/ethnicity, decision role preference, clinical characteristics).

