4.1 Study Outcomes

- **Knowledge:** Similar to knowledge items used when designing DAs[37-39] and assessing decision quality[40], we will develop knowledge items based on information that is considered essential to making treatment decisions (e.g. understanding terms, understanding facts that differentiate options)[41]. Questions will be asked using true/ false/ unsure responses. Total number of correct responses to the items will be calculated. One point will be given for each correct response and zero for unsure or incorrect responses; answers will be expressed as percent correct. Similar scales have been used in other DA trials [38, 39] and have good internal consistency (Cronbach's alpha coefficients range from 0.82 – 0.83) [37].

Decisional Conflict: The Decisional Conflict Scale [42] (DCS) is a validated and widely-used measure of uncertainty about decisions. We will administer the 4-item SURE Test version of the DCS [42] to assess whether individuals feel they have enough information to make a choice, are clear about their values for risks and benefits of their choice, and feel they have enough support to make a choice. Items are scored as 1 (yes) or 0 (no). If the total score is less than 4, it indicates the probability that a patient experiences clinically significant decisional conflict.

- **Decision Self-Efficacy:** We will use the lower literacy version of the Decision Self-Efficacy Scale [43], a validated measure of an individual's self-confidence or belief in their ability to make a decision. Individuals are asked to rate on a three-item scale how confident they feel taking actions involved in making an informed choice (e.g., gathering information, asking questions, and expressing opinions). This scale has been validated and used to study health literacy and shared decision making among patients and lower SES populations among others [43-46]. It has high levels of internal consistency (mean Cronbach's alpha = 0.86) [43] and correlates with feeling informed, supported, and knowledgeable about decisions [43].

- **Usability:** After participants use the DA, they will complete the 10-item System Usability Scale (SUS [47]) to measure the DA's usability. We will also ask clinicians to fill out this measure after the end of the study.

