6.1.1 Administrative Procedures

6.1.1.1 Recruitment and Procedures

Aim 2- The goal of Aim 2 is to pilot test the DA to determine its efficacy and the likelihood of using it in routine practice. Eligible patients will be determined by the outpatient EMR (AllScripts). Once patients have been identified, their hepatologist or nephrologist will briefly describe the project and gauge patients' interest in participating. The project coordinator will then reach out to interested patients to describe the project in further detail and obtain informed consent. Patients will complete a brief pre-test questionnaire assessing socio-demographics, health literacy, knowledge, decisional conflict, and decision self-efficacy. All measures were chosen based on their short length so as not to burden participants. We have used a similar recruitment strategy and measures in past projects, and the procedures did not disrupt patient flow or introduce burden on patients [35, 36]. We will document CKD stage, dialysis status (yes/no), stage of fibrosis of the liver, whether or not the patient has tried using a DAA in the past to treat HCV, and presence of comorbidities (diabetes, heart disease, high blood pressure, HIV) to use for tailoring health information in the decision tool. This information will be collected from patients and clinicians and verified in the medical record with patients' consent.

Next, we will provide patients with the DA through tablet PCs on-site, brief training on how to use the tablets, and we will allow patients to view the DA. Patients can opt to view it on paper if they are uncomfortable with computers. They can take home a printed summary of the information to review at home before meeting with their clinician. The summary will also be placed in the patient's chart. After viewing the DA, patients will complete post-test measures of knowledge, decisional conflict, and decision self-efficacy. Recruitment will occur over 12 months. Patients will be provided with a \$20 gift card for participation and will have the added benefit of using the DA. We anticipate the pilot test to take about 30-45 minutes.

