8.1 Statistical Methods

Aim 2 Analytic Methods: For all analyses, descriptive statistics (e.g., frequencies, tendencies, variability) and diagnostic plots will be completed on all variables. Data will be examined for outliers and tested as appropriate for normality, linearity, and homoscedasticity. Appropriate corrective strategies, such as transformations, use of robust methods, or data reduction, will be used if problems are identified. These preliminary analyses are necessary to ensure high quality data and to test assumptions of the proposed models. We will also compare basic demographic and clinical characteristics between study enrollees and eligible refusers to characterize the representativeness of the included patients. We will also examine within group differences in our outcomes (knowledge, decisional conflict, decision self-efficacy) among patients pre- and post-use of the DA in a multivariable linear regression model controlling for up to 5 independent covariates (e.g. age, stage of fibrosis, health literacy). We intend to include knowledge, decisional conflict, and decision self-efficacy as primary outcomes in three separate multivariable models, age and stage of fibrosis as planned covariates in all models. Health literacy will be included as a covariate in the model with knowledge as an outcome. Others will be added if significant at the bivariate level. The knowledge scale that we develop will be pilot tested with patients as well. We will assess scale reliability using Cronbach’s alpha.

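### Section 8.3 supports N=70 with a 15-point fall in decisional conflict, which the 0 to 4 SURE total in section 4.1 cannot show; N=70 still fits the effect size of 0.35

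*Combined protocol and SAP*

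**What the plan says.** Section 4.1 introduces the Decisional Conflict Scale and then names the version patients will complete: "We will administer the 4-item SURE Test version of the DCS". The scoring follows: "Items are scored as 1 (yes) or 0 (no). If the total score is less than 4, it indicates the probability" of decisional conflict. Section 6.1.1.1 lists decisional conflict before and after use of the decision aid, names no other instrument, and explains the choice of questionnaires: "All measures were chosen based on their short length so as not to burden participants".

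Section 8.3 derives the sample size from the change expected in decisional conflict. It cites past decision-aid studies and a user manual, which item 55 of the reference list identifies as the manual for the Decisional Conflict Scale. The expectation reads: "We expect a 15 point reduction in decisional conflict scores pre- and post- use of the DA and an effect size of 0.35". The test is named: "To examine within group differences in decisional conflict among patients pre- and post-use of the DA, we will conduct a paired-samples t-test". The result is: "A sample size of 70 patients allows us to achieve a power of 80%, using two-sided t-test with a type I error of 5" per cent. Section 8.3 gives no score range, no SD and no definition of the SD behind 0.35.

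Section 8.1 makes decisional conflict one of three primary outcomes: "We intend to include knowledge, decisional conflict, and decision self-efficacy as primary outcomes in three separate multivariable models". It is the only one of the three with a power statement.

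**The concern.** Sections 4.1 and 8.3 appear to describe different scores. The scale-unit input in 8.3 is a fall of 15 points. The instrument in 4.1 has four yes/no items, and its total moves upward when conflict lessens.

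The expected change is what ties a standardised effect size to something a patient or clinician would recognise. If it belongs to another score, the reader cannot say what change in SURE points the study is sized to detect, or why 0.35 is a reasonable expectation for a four-item total. The observed result also cannot be set against the planned one, because a benefit would appear as a rise of at most 4 points against a planned fall of 15. Section 3.2 says these pilot data precede a randomised trial, so an undefined effect metric could carry into that trial's planning.

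**Working it through.** **Inputs.** From 8.3: n = 70, two-sided 5%, 80% power, paired t-test, 15-point reduction, effect size d = 0.35. From 4.1: four items, each scored 0 or 1, with a total below 4 signalling conflict.

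**1. The plan's own figure.** Take d as the mean paired change divided by the SD of the paired change, the standardiser that a paired t-test uses. Power comes from the noncentral t with n − 1 degrees of freedom and noncentrality d√n.

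- At n = 70 and d = 0.35, noncentrality is 0.35 × √70 = 2.93 and power is 82.3%.
- The smallest n for 80% at d = 0.35 is 67 (n = 66 gives 79.99%, n = 67 gives 80.6%).
- The effect detectable with 80% power at n = 70 is 0.3396, or 0.34 SD.
- As a check, the normal approximation gives ((1.960 + 0.842)/0.35)² = 64.1, so 65.

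Seventy is therefore slightly more than 0.35 requires. An effect of 0.34 gives exactly 70. The plan errs, if at all, on the safe side. The 15 points do not enter this calculation.

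**2. Range and direction of the administered score.** These are derived from the scoring rule rather than stated outright. Four items at 0 or 1 give a total from 0 to 4. Because a total below 4 signals conflict, a higher total is better. A change score lies between −4 and +4.

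**3. Do 15 points and 0.35 fit that score?**

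- A change of 15 points lies outside −4 to +4.
- Together the two figures imply an SD of 15/0.35 = 42.9 points. The largest possible SD is 2 for a single 0 to 4 total and 4 for a change between −4 and +4.

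Neither figure can describe the SURE total, whichever SD was meant.

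**4. Would a rescaled score rescue it?** If SURE were reversed and expressed on 0 to 100 (an assumption; no section says so), 15 points would be 15 × 4/100 = 0.6 SURE points and 42.9 would be 42.86 × 4/100 = 1.71 SURE points. On any 0 to 100 score, an SD of change of 42.9 is arithmetically possible, since the bound at a mean change of 15 is √(100² − 15²) = 98.9. The documents do not show that either was intended.

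**5. What 0.34 SD means in SURE points.** This needs the SD of the SURE change, which the documents do not give. For illustration only, assumed SDs of 1.0, 1.5 and 2.0 give 0.34, 0.51 and 0.68 points.

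**The case against.** The strongest reply is that 0.35 alone determines power, so removing the 15 points changes neither N nor the stated 80%. That is correct, and it limits the point. But 8.3 offers the expected change as the ground for its calculation, and nothing else in the documents supports 0.35 for a four-item total.

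A second reply is that 8.3 was plainly written for the longer scale, since it cites that scale's manual. This probably explains how the mismatch arose. It confirms the mismatch rather than removing it, because 4.1 administers only the short version.

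A third is that a reduction in decisional conflict is ordinary language for the construct. That is fair: the direction follows from the same mismatch and is not a separate error.

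A reader might go further and infer that the 80% power is itself in doubt, because 0.35 could be in SDs of a single measurement. With equal SDs before and after, the paired effect would be 0.35/√(2(1 − ρ)), and power at n = 70 would be 53%, 68%, 82% or 96% at assumed correlations of 0, 0.3, 0.5 or 0.7. No passage suggests that reading. Section 8.3 names a paired test, and the single-measurement reading gives the stated 80% only near ρ = 0.47, where it almost coincides with the paired one. Nor do the documents support calling 0.35 unsuitable: the sources behind it were not available for this review.

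**Conclusion.** The inconsistency holds on the text. The expected change in 8.3 cannot occur on the instrument in 4.1 (15 points against a maximum of 4), and the implied SD of 42.9 exceeds the largest possible SD of change, which is 4. The sample size and stated power are not arithmetically wrong: 70 patients give 82% power for 0.35 SD of the paired change and 80% for 0.34 SD. What is lost is the meaning of the planned effect in SURE points and the stated reason for expecting 0.35.

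The conclusion rests on the 0 to 4 range and the direction derived from 4.1. The power figures also rest on reading 0.35 as SDs of the paired change. The consequence is limited. This is a single-arm pilot whose results section 8.2.3 already presents as preliminary, and the observed change can still be reported with its confidence interval. It should be fixed because one of three primary outcomes, the only one with a power statement, has a design figure that is wrong as written.

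**What to change.** Keep N = 70 and the paired t-test, and reconcile 4.1 with 8.3 before analysis.

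**If SURE is the outcome**, delete the 15-point reduction and state the basis for 0.35. Wording for 8.3 could be: *Decisional conflict is the SURE total (0 to 4; an increase is an improvement). The effect size is in SDs of the paired change. With 70 patients, a two-sided 5% paired t-test has 80% power for a mean change of 0.34 SD (82% for 0.35 SD).* Then add the sponsor's own SD of change for SURE, with its source, and convert 0.34 SD to SURE points. The SDs used for illustration above come from no passage and should not go into the protocol.

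**If a longer or 0 to 100 rescaled score was intended**, correct 4.1 to name it with its range, direction and SD of change, and reconcile 15 points with 0.35, which together imply an SD of 42.9.

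The cost is rewording, with no extra patients and no change of test. The exception is a longer scale, which would lengthen the questionnaire and sit awkwardly with the aim of brevity in 6.1.1.1.

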9 ADMINISTRATIVE AND REGULATORY DETAILS

Because we have a fully executed contract that has been reviewed by legal teams from both Merck and Washington University, to the extent that any part of the protocol conflicts with the contract, the contract will control decisions.

9.1 Confidentiality

The research team understands that the protection of participants is of the utmost importance when conducting research with human subjects. In order to protect the rights and safety of participants, we will comply fully with the Code of Federal Regulations Title 45 Public Welfare, Department of Health and Human Services, National Institutes of Health, and Office for Protection from Research Risks, Part 46 Protection of Human Subjects. All aspects of the research projects (protocol, questionnaires, and recruitment materials) will be submitted to and reviewed by the Washington University institutional review board.

9.1.1 Confidentiality of Data

By signing this protocol, the investigator affirms to the Sponsor that information furnished to the investigator by the Sponsor will be maintained in confidence, and such information will be divulged to the Institutional Review Board, Ethics Review Committee or similar or expert committee; affiliated institution and employees, only under an appropriate understanding of confidentiality with such board or committee, affiliated institution and employees. Data generated by this study will be considered confidential by the investigator, except to the extent that it is included in a publication as provided in the Publications section of this protocol.

Data and Safety Monitoring Plan: The PI and study team will be responsible for ongoing and continuous monitoring of human participants in the study, as guided by the Human Research Protection Office (HRPO) at the Washington University School of Medicine (WUSM). A data safety monitoring plan (DSMP) has been developed in conjunction with WUSM. This is a minimal risk study and we do not anticipate safety concerns. DSMP components for this project include: IRB approval from institution; standard continuing review via IRB; all members of research team will complete university IRB training; and human subjects concerns as a standard agenda item for project meetings. Any adverse events will be reported to HRPO following WUSM procedures (i.e., within 7 calendar days for events other than serious health events) and to the study sponsor in accordance with Section 7.0. There is no penalty for refusing to participate or complete components of the study. The research team will discuss the logistics, safety issues, and mechanics of the study on a bi-weekly basis.

9.1.2 Confidentiality of Subject Records

By signing this protocol, the investigator agrees that the Sponsor (or Sponsor representative) or Institutional Review Board/Independent Ethics Committee (IRB/IEC), may consult and/or copy study documents in order to verify worksheet/case report form data. By signing the consent form, the subject agrees to this process. If study documents will be photocopied during the process of verifying worksheet/case report form information, the subject will be identified by unique code only; full names/initials will be masked prior to transmission to the Sponsor.

By signing this protocol, the investigator agrees to treat all subject data used and disclosed in connection with this study in accordance with all applicable privacy laws, rules and regulations.

Protection against risks: Study materials, including qualitative interview guide and survey items and scales will be selected to reduce burden to participants. In order to protect confidentiality, all written information and questionnaires will be kept separately from identifiable information in a locked cabinet. Identification data will be stored in a separate locked cabinet linked with participants' confidential ID numbers. Data will be organized and analyzed base on participants' ID numbers. All electronic files will be saved on a computer network which requires authorization from the Systems Manger to view, and individual files will also be password protected. All members of the research will have completed HIPAA and CITI training and will handle data with complete confidentiality. The only identification that will appear on any data collection instruments with project participants will be a participant identification code. Data will be reported in summary format only, with no individual characteristics shared.

9.1.3 Confidentiality of Investigator Information

By signing this protocol, the investigator recognizes that certain personal identifying information with respect to the investigator, and all subinvestigators and study site personnel, may be used and disclosed for study management purposes, as part of a regulatory submissions, and as required by law. This information may include:

- name, address, telephone number and e-mail address;
- hospital or clinic address and telephone number;
- curriculum vitae or other summary of qualifications and credentials; and
- other professional documentation.

Consistent with the purposes described above, this information may be transmitted to the Sponsor, and subsidiaries, affiliates and agents of the Sponsor, in your country and other countries, including countries that do not have laws protecting such information. Additionally, the investigator's name and business contact information may be included when reporting certain serious adverse events to regulatory agencies or to other investigators. By signing this protocol, the investigator expressly consents to these uses and disclosures.

If this is a multicenter study, in order to facilitate contact between investigators, the Sponsor may share an investigator's name and contact information with other participating investigators upon request.

9.2 Compliance with Financial Disclosure Requirements

Financial Disclosure requirements are outlined in the US Food and Drug Administration Regulations, Financial Disclosure by Clinical Investigators (21 CFR Part 54). It is the Sponsor's responsibility to determine, based on these regulations, whether a request for Financial Disclosure information is required. It is the investigator's/sub investigator's responsibility to comply with any such request.

The investigator/sub investigator(s) agree, if requested by the Sponsor in accordance with 21 CFR Part 54, to provide his/her financial interests in and/or arrangements with the Sponsor to allow for the submission of complete and accurate certification and disclosure statements. The investigator/sub investigator(s) further agree to provide this information on a Certification/Disclosure Form, commonly known as a financial disclosure form, provided by the Sponsor or through a secure password-protected electronic portal provided by the Sponsor. The investigator/sub investigator(s) also consent to the transmission of this information to the Sponsor in the United States for these purposes. This may involve the transmission of information to countries that do not have laws protecting personal data.

